The patients in the prospective period will have a final visit (**visit 3**), that is scheduled to occur at least 3 months but preferably no more than 4 months after visit 2, i.e. maximum 10 months after the baseline visit. During visit 2 and visit 3, the patients will be asked to fill out two QoL questionnaires again (EQ-5D and KCCQ) and a final NT-proBNP measurement will be obtained.

***Note:** Within this study, clinically stable patients are defined as those patients, who by the judgement of their primary care physician currently do not require and, in the last 3 months prior to the baseline visit have not had, any change in their pharmacological or device treatment of HF.

Figure 3-1 Study design

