5.6.2 Withdrawal of informed consent

Patients/subjects may voluntarily withdraw consent to participate in the study for any reason at any time. Withdrawal of consent from the study is defined as when a patient:

- Does not want to participate in the study anymore
and
- Does not want any further visits or assessments
and
- Does not want any further study related contacts
and
- Does not allow analysis of already obtained biologic material

In this situation, the investigator must make every effort (e.g. telephone, e-mail, letter) to determine the primary reason for the patient's decision to withdraw his/her consent and record this information.

Further attempts to contact the patient are not allowed unless safety findings require communicating or follow-up.

All efforts should be made to complete the assessments prior to study withdrawal. A final evaluation at the time of the patient's study withdrawal should be made as detailed in [Table 6-1](#).

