5.6.4 Early study termination by the sponsor

The study can be terminated by Novartis at any time for any reason. This may include reasons related to practical issues, or for regulatory or medical reasons (including slow enrolment). Should this be necessary, the patient must be seen as soon as possible and treated as a prematurely withdrawn patient. The investigator may be informed of additional procedures to be followed in order to ensure that adequate consideration is given to the protection of the patient's interests. The investigator will be responsible for informing the Institutional Review Board/Independent Ethics Committee (IRBs/IECs) of the early termination of the trial.

6 Visit schedule and assessments

The study comprises 3 visits: baseline (Visit 1), Visit 2 (recommended max. 6 months after baseline), Visit 3 (recommended at least 3 months and preferably not later than 4 months after Visit 2; max. 10 months after baseline). At baseline (Visit 1) all consecutive CHF patients who satisfy all inclusion and exclusion criteria should be documented and should complete the QoL questionnaires. At this visit, the investigator will assess whether the patient's status is considered clinically stable (as defined in [Section 2.1](#)) and document his/her decision. Thereafter all patients will undergo blood-sampling for on-site NT-proBNP measurement. Only patients considered clinically stable and with NT-proBNP levels ≥ 600 pg/ml will be referred to a cardiologist for evaluation of treatment optimization. After the visit to the cardiologist, but no later than 6 months after the baseline visit, the patient should return to the investigator's office for Visit 2. At Visit 2, the patient should complete the QoL questionnaires and the cardiologist's recommendations will be reviewed and documented by the investigator; at this visit, the investigator should document, if the cardiologist's recommendations or changes for the patient's HF-treatment will be followed or continued, respectively. The investigator should provide reasons if the recommendations are not followed and document the prescribed HF treatment. At Visit 3, maximally 10 months after baseline, but no earlier than 3 months after Visit 2, the patient should return for the final visit, where clinical and QoL outcomes will be documented and thereafter the patient will undergo blood sampling for measurement of NT-proBNP levels.

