[Table 6-1](#) lists all of the assessments and indicates with an "x" when the visits are performed.

Missed or rescheduled visits should not lead to automatic discontinuation. Patients/subjects who prematurely discontinue the study for any reason should be scheduled for a visit as soon as possible, at which time all of the assessments listed for the final visit will be performed. At this final visit, the adverse events and concomitant medications are reconciled on the CRF.

Table 6-1 Assessment schedule

Visit number	Visit 1	Visit 2	Visit 3
Time of Visit and recommended visit windows	Baseline	After referral (max. 6 months after baseline)	Min. 3 months, max 4 months after visit 2 (max. 10 months after baseline)
Informed consent	X		
Inclusion/exclusion criteria	X		
Demographic and clinical history (incl. diagnostic and therapeutic procedures)	X	X ¹	X ¹
Height	X		
Body weight	X		X ¹
Physical examination incl. NYHA-Status and vital signs	X	X ¹	X ¹
Observation of ongoing drug/ non-drug treatment for HF	X	X ¹	X ¹
Observation of relevant laboratory tests, as available per routine care	X	X ¹	X ¹
EQ-5D questionnaire	X	X ¹	X ¹
KCCQ questionnaire	X	X ¹	X ¹
Assessment and documentation of clinical stability of patient (as per Section 2.1)	X		
NT-proBNP assessment	X		X ¹
Referral to cardiologist ¹	X ¹		
Recording of specialist advice/prescription on drug/ non-drug treatment modification ¹		X ¹	
Prescription and documentation of revised treatment in the discretion of primary care physician ¹		X ¹	
Observation of comorbidities and their changes during the study	X	X ¹	X ¹
Adverse events	X	X ¹	X ¹
Report adverse drug reactions to any medication and incidents with medical devices as per local regulations	X	X ¹	X ¹

¹ Applies only for patients who enter the prospective period, i.e. clinically stable patients with NT-proBNP ≥ 600 pg/ml

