4.2 Study population

According to the protocol, it was planned to enroll a total of 4000 CHF patients of which approximately 2400 are estimated to enter the prospective period (who are considered clinically stable and show NT-proBNP levels ≥ 600 pg/ml). The recruitment was to be regarded as completed once approximately 2400 patients have entered the prospective period irrespectively how many patients have been enrolled totally.

However, it was decided by Novartis to determine the study prematurely, i.e. to stop recruiting and data collection in March 2018: therefore, last patient first visit was on 07 March 2018, last patient last visit on 23 March 2018. This means, that not every subject was able to perform Visit 3 of the study.

Patients/subjects eligible for inclusion in this study had to fulfil all of the following criteria:

- Willing and able to provide written informed consent and accept study procedures and time schedule.

- Age \geq 18 years.
- Patients suffering from chronic heart failure (the heart failure diagnosis must have been made or confirmed by a cardiologist and/or hospital physician at any time in the patient's medical history).
- Patients with reduced ejection fraction ($\leq 40\%$) as confirmed at any time point in the patient's medical history.

Patients/subjects fulfilling any of the following criteria were not eligible for inclusion in this study.

- Use of investigational drugs either within 5 half-lives of enrollment, or within 30 days, or until the expected pharmacodynamic effect has returned to Baseline, whichever is longer.
- Major surgery in the last 3 months prior to Baseline or planned major surgery or cardiac intervention during the study.
- Cancer or other significant co-morbidities implying that the patient's condition is unstable.
- Comorbidities that can be associated with elevated natriuretic peptide (NP) levels: renal insufficiency (eGFR < 30 ml/min/1.73 m² calculated according to MDRD formula), recent (less than 3 months) cerebral trauma or recent (less than 3 months) cerebrovascular incident, novel diagnosis or acute exacerbation of COPD within the last 3 months.
- Patients who are primarily managed and regularly followed-up by a cardiologist for their HF
- Highly frail patients whose estimated lifespan due to comorbidities by the judgement of the investigator is less than 6 months.

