4.4 Study schedule

The study comprised 3 visits: Baseline (Visit 1), Visit 2 (recommended max. 6 months after Baseline), Visit 3 (recommended at least 3 months and preferably not later than 4 months after Visit 2; max. 10 months after Baseline). At Baseline (Visit 1) all consecutive CHF patients who satisfied all inclusion and exclusion criteria were to be documented and should complete the QoL questionnaires. At this visit, the investigator assessed whether the patient's status was considered clinically stable (as defined in Section 3.1) and documented his/her decision. Thereafter, all patients underwent blood-sampling for on-site NT-proBNP measurement. Only patients considered clinically stable and with NT-proBNP levels ≥ 600 pg/ml were referred to a cardiologist for evaluation of treatment optimization. After the visit to the cardiologist, but no later than 6 months after the Baseline visit, the patient should return to the investigator's office for

Visit 2. At Visit 2, the patient should complete the QoL questionnaires and the cardiologist's recommendations was reviewed and documented by the investigator; at this visit, the investigator should document, if the cardiologist's recommendations or changes for the patient's HF treatment were followed or continued, respectively. The investigator should provide reasons if the recommendations were not followed and document the prescribed HF treatment. At Visit 3, not later than 10 months after Baseline, but no earlier than 3 months after Visit 2, the patient should return for the final visit, where clinical and QoL outcomes were documented. Thereafter, the patient underwent blood sampling for measurement of NT-proBNP levels.

[Table 4-1](#) lists all of the assessments and indicates with an "x" when the visits were performed.

Table 4-1 Assessment schedule

Visit number	Visit 1	Visit 2	Visit 3
Time of Visit and recommended visit windows	Baseline	After referral (max. 6 months after Baseline)	Min. 3 months, max 4 months after visit 2 (max. 10 months after Baseline)
Informed consent	X		
Inclusion/exclusion criteria	X		
Demographic and clinical history (incl. diagnostic and therapeutic procedures)	X	X ¹	X ¹
Height	X		
Body weight	X		X ¹
Physical examination incl. NYHA-Status and vital signs	X	X ¹	X ¹
Observation of ongoing drug/ non-drug treatment for HF	X	X ¹	X ¹
Observation of relevant laboratory tests, as available per routine care	X	X ¹	X ¹
EQ-5D questionnaire	X	X ¹	X ¹
KCCQ questionnaire	X	X ¹	X ¹

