7.6 NT-proBNP

NT-proBNP will be analysed at Visit 1 for the Enrolled Set, stratified by inclusion into the prospective period of the study, and at Visit 1 and Visit 3 for the Follow-up Set, and additionally stratified by adherence to ESC guidelines before and after referral to cardiologist.

Summary statistics for NT-proBNP at Visit 1, Visit 3 and the absolute change from Visit 1 to Visit 3 will be provided. In case an interval is given for the NT-proBNP result, the following rules will be applied: if the value is estimated downwards (i.e. “ $<$ XX pg/ml”), the new value XX-1 pg/ml will be used for the analysis. If the value is estimated upwards (i.e. “ $>$ XX pg/ml”), the new value XX+1 pg/ml will be used for the analysis.

In addition, NT-proBNP in groups (\geq 600 to $<$ 800 pg/ml, \geq 800 to $<$ 1000 pg/ml, \geq 1000 to $<$ 1200 pg/ml, \geq 1200 pg/ml to $<$ 1400 pg/ml, \geq 1400 pg/ml to $<$ 1600 pg/ml, \geq 1600 pg/ml to $<$ 1800 pg/ml, \geq 1800 pg/ml to $<$ 2000 pg/ml, \geq 2000 pg/ml) will be displayed by visit.

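### SAP 7.6 and 7.7 analyse every Visit 3 value whatever its interval, although the early-stop rules can produce final visits less than 3 months after Visit 2

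*SAP*

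**What the plan says.** **Timing of Visit 3.** Protocol 3.1 schedules it "at least 3 months but preferably no more than 4 months after visit 2, i.e. maximum 10 months after the baseline visit". SAP 4.4 repeats the limits: "At Visit 3, not later than 10 months after Baseline, but no earlier than 3 months after Visit 2".

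**Early stop.** Protocol 5.6.4 says that on termination by the sponsor "the patient must be seen as soon as possible and treated as a prematurely withdrawn patient". Protocol section 6 says that, whatever the cause, patients who leave early "should be scheduled for a visit as soon as possible, at which time all of the assessments listed for the final visit will be performed". Table 6-1 has no early-termination column. Visit 3 is its only final visit, and the assessments there include NT-proBNP, EQ-5D and KCCQ.

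**What happened.** SAP 4.2 records the stop: "last patient first visit was on 07 March 2018, last patient last visit on 23 March 2018". The only consequence it names is that some subjects could not have a Visit 3.

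**Analysis.** SAP 7.6 states: "Summary statistics for NT-proBNP at Visit 1, Visit 3 and the absolute change from Visit 1 to Visit 3 will be provided". It stratifies these results by guideline adherence before and after referral. SAP 7.7 analyses the questionnaires by visit label. Neither section gives a visit window, a rule for classifying a termination visit, or a sensitivity analysis by interval. SAP 7.2 summarises the time from Visit 2 to Visit 3 but does not use it to select or group values. SAP 7.10 drops a change only when a value is missing. SAP 7.13 lists no deviation on this point.

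**The concern.** Two rules in the protocol pull in different directions once the study is stopped. One asks for at least 3 months between Visit 2 and Visit 3; the other asks for the same assessments promptly. A site that followed the stop rule could take the final NT-proBNP sample and questionnaires days or weeks after Visit 2. The SAP was written with the stop known, yet it would pool such values with those taken on schedule.

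Two secondary objectives depend on Visit 3: how treatment optimization affects NT-proBNP, and the course of quality of life after referral. Table 2-1 of the protocol relates the NT-proBNP change to baseline treatment and to the decision taken at Visit 2. The time since Visit 2 is therefore a large part of the exposure being compared. Early values arising from the stop would come mainly from late-enrolled patients, so pooling would also mix calendar time with length of follow-up.

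**Working it through.** **1. The plan's own schedule.** Latest Visit 2 at 6 months plus at most 4 months to Visit 3: 6 + 4 = 10 months. This reproduces the stated maximum.

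**2. Dates (SAP 4.2).**
- Last first visit to last last visit: 7 to 23 March 2018 = 16 days.
- Latest Visit 2 that allows a 3-month interval: 23 March 2018 minus 3 months = 23 December 2017 (22 December if 3 months is taken as 91 days).
- A patient with Visit 2 after that date has no Visit 3 or one at less than 3 months.

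**3. Effect of pooling.** Let f be the share of Visit 3 values that are early, g the share of the full change already reached at those readings, and D the full change. The pooled mean is (1 − f)D + f·g·D, so

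observed / full = 1 − f(1 − g).

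The documents give neither f nor g. Both are assumptions here:

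| f | g = 0 | g = 0.5 | g = 1 |
|---|---|---|---|
| 10% | 0.90 | 0.95 | 1.00 |
| 20% | 0.80 | 0.90 | 1.00 |
| 40% | 0.60 | 0.80 | 1.00 |

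To read the ratio as a difference between adherence strata, f and g must also be the same in the strata compared.

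**4. Is 10% to 40% a reasonable range for f?** Assume uniform enrolment over T months up to 7 March 2018, a fixed lag of L months from Visit 1 to Visit 2, an early final visit for every patient past Visit 2, and a Visit 3 for everyone who had time for one. At 23 March the time since Visit 1 runs from 16/30.4 = 0.53 months to T + 0.53 months. The early share of Visit 3 values is then

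f = 3 / (T + 0.53 − L).

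- T = 24 (the planned enrolment period): L = 1 gives 3/23.53 = 13%; L = 6 gives 3/18.53 = 16%.
- T = 12: L = 1 gives 3/11.53 = 26%; L = 6 gives 3/6.53 = 46%.

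The enrolment start date is not given, so T is unknown. The illustration spans about 13% to 46%, close to the assumed range. It shows what the stop rules could produce, not what happened.

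**5. With the restriction.** Among values at least 3 months after Visit 2, f = 0 and the ratio is 1.

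**The case against.** **No early visit is documented.** SAP 4.2 speaks only of Visit 3s that could not take place. Nothing says that termination visits were made or entered as Visit 3. This stands, and the point is conditional on it.

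**Early readings may already show an effect.** A reader might infer that a value taken soon after Visit 2 cannot reflect the new treatment. The documents do not support that. The NT-proBNP change runs from Visit 1. The cardiologist may change treatment before Visit 2 (Protocol 3.1; SAP 7.4.3 analyses this), and Visit 2 may follow that consultation by up to 4 weeks. The plan itself reports quality-of-life change from baseline to Visit 2. A fall in NT-proBNP through regression to the mean, after selection at 600 pg/ml or more, also needs no 3-month wait.

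**The share affected is easily overstated.** A reader might set the 10-month maximum against 24 months of enrolment and conclude that 10/24 = 42% are affected. That counts patients not guaranteed the longest permitted schedule, not early readings. Visit 2 has no minimum interval, so many patients can finish on schedule well before 10 months.

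**The purpose of the 3 months is not stated.** Protocol section 6 also calls the interval recommended in one sentence and sets it as a minimum in another.

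**Part of this is visible already.** SAP 7.2 gives the interval summary, protocol deviations and discontinuations. That would reveal that short intervals exist, but not how many values are early or whether the results depend on them.

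**A restricted analysis selects too.** It removes mainly late-enrolled patients. This stands, and argues for showing both analyses rather than replacing one with the other.

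**Conclusion.** The gap is real, and closing it is a cheap improvement. The protocol's stop rules and the 3-month minimum together allow a mixed follow-up interval at Visit 3, and SAP 7.6 and 7.7 have no rule for it. The dates are firm: with Visit 2 after about 23 December 2017, Visit 3 is absent or early.

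Dilution is possible, not shown. It requires that early final visits took place, were recorded as Visit 3, and preceded the full response. Its size is unknown: from none (g = 1) to a ratio of 0.60 (40% early, no response yet), under assumed values.

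The scope is limited. The argument about adherence strata applies to NT-proBNP only, because SAP 7.7 does not specify that stratification for quality of life. There the risk is a blurred time course. The strata are not randomised and are only described, so no test is at stake. Adherence at Visit 3 (A3) classifies the prescriptions in force at a visit rather than a lagged response, so the argument does not extend to it. The primary endpoint, adherence at Visit 2 (A2), does not depend on the timing of Visit 3.

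**What to change.** In SAP 7.6 and 7.7:

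1. State how a final visit made early, because of the sponsor stop or another discontinuation, is mapped to Visit 3. Cover patients stopped before any Visit 2.
2. Report the number of Visit 3 NT-proBNP and questionnaire values taken less than 3 months after Visit 2.
3. Present the Visit 3 values and changes twice: for all final-visit values, and for those at least 3 months after Visit 2, with a stated tolerance. Give the number excluded from the second.

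The interval is already a derived variable (SAP 6.5), so this needs SAP wording and a date filter; SAP 7.12 provides for an addendum. If no early visits exist, the filter excludes nobody. If they do, the window is fixed before results are seen. The cost is extra tables and a smaller subset that under-represents late-enrolled patients, which the report should say.

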Study design	
This is a low-interventional, prospective, study enrolling patients with chronic heart failure who are managed in the primary care setting across Europe. The study comprises three visits over a period of maximum 10 months. Enrollment is planned to last 24 months.
 
At baseline (visit 1) for all consecutive patients, who satisfy the inclusion and exclusion criteria, the demographic and clinical characteristics, their current therapy regimen for the treatment of HF, any concomitant medication and their baseline QoL will be documented (EQ-5D, KCCQ). At this visit, after the investigator documents his/her decision whether the patient is considered being clinically stable, all patients (clinically stable and not stable) will have a blood test for assessing NT-proBNP levels.
 
Only patients who are considered being clinically stable by the investigator and who show NT-proBNP blood levels ≥ 600 pg/ml will enter the prospective period of the study.
 
The Patients will be referred to a cardiologist for evaluation of their HF treatment. After the referral visit to the specialist's office, the patient will return to the primary care physician for visit 2. During visit 2 the primary care physician will evaluate and record the recommendations provided or treatment changes introduced by the specialist and will make and record his/her decision on the patient's future HF treatment. In addition, EQ-5D and KCCQ questionnaires will be filled out by the patient at this visit.
 
The patients in the prospective period will have a final visit (visit 3), where they will be asked to fill out two QoL questionnaires (EQ-5D, KCCQ) again, will have their vital signs and medication documented and a final NT-proBNP measurement will be obtained.

Population	The study population will consist of adult (≥ 18 years) male and female patients with chronic heart failure with reduced ejection fraction (LVEF $\leq 40\%$) who are currently managed in a primary care setting in sites across Europe.

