2.2 Secondary objective(s)

- To describe the baseline demographic and clinical characteristics, as well as pharmacological and device treatment of CHF patients managed in the primary care setting (in the total population of enrolled patients and also sub-grouped into different European country and patient characteristics clusters).
- To assess in clinically stable patients the impact of patients' key baseline characteristics on the cardiologists' and primary care physicians' prescription practice for HF treatment and the adherence of these treatment choices to the recommendations of the current ESC guidelines.

- To describe the blood levels of NT-proBNP in CHF patients managed in the primary care setting.
- To describe the proportion of CHF patients managed in the primary care setting considered as being clinically stable according to the above definition ([Section 2.1](#)).
- To describe local prescription practice of cardiologists for the treatment of clinically stable CHF patients with NT-proBNP levels ≥ 600 pg/ml.
- To describe local prescription practice and decision making of primary care physicians for the treatment of clinically stable CHF patients with NT-proBNP levels ≥ 600 pg/ml.
- To characterize how treatment optimization, defined as prescription of treatment regimens adherent to the recommendations of the ESC guidelines affects NT-proBNP levels in clinically stable CHF patients with baseline NT-proBNP levels ≥ 600 pg/ml.
- To assess the baseline health-related quality of life (QoL) in CHF patients and describe the temporal course of QoL after specialist referral in clinically stable CHF patients with NT-proBNP ≥ 600 pg/ml by means of EuroQol EQ-5D and KCCQ questionnaires.

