To demonstrate that treatment optimization, defined as prescription of treatment regimen adherent to the recommendations of the ESC guidelines will lead to clinically relevant decrease of NT-proBNP levels in	
Title: NT-proBNP levels in clinically stable patients at Visit 3
 
Title: Change of NT-proBNP levels in clinically stable CHF patients with and without treatment optimization at Visit 2
 
Description: At the Visit 3 (end of study) NT-proBNP will again be assessed in clinically stable CHF patients with baseline NT-proBNP levels ≥ 600 pg/ml. Thus, for those patients two NT-proBNP measurements will be available: at baseline and at visit 3. The individual change of NT-proBNP between both time points will be assessed in accordance to the patients' treatment history during the study, i.e. baseline HF treatment and therapeutic decision taken at Visit 2.
	Section 9.5.3

OBJECTIVE	Endpoint Title, Description and Reporting Time Frame for analysis and Unit of Measure	Stat Analysis Section
clinically stable CHF patients with baseline NT-proBNP levels \geq 600 pg/ml.	Units: Descriptive statistics for quantitative data, absolute and relative frequency distributions for treatment history subgroups Time frame: Baseline (Visit 1) and Visit 3	
To assess the baseline health-related quality of life (QoL) in CHF patients and describe the temporal course of QoL after specialist referral in clinically stable CHF patients with NT-proBNP \geq 600 pg/ml	Title: Change of EQ-5D total and individual sub-scores between Visit 3, Visit 2 and baseline Title: Change in KCCQ total and individual sub-scores between Visit 3, Visit 2 and baseline Title: Baseline EQ-5D total and individual sub-scores Title: Baseline KCCQ total and individual sub-scores Description: At baseline (all patients) and at Visit 2 and Visit 3 (only patients who have entered the prospective period of the study, i.e. clinically stable patients with a NT-proBNP level \geq 600 pg/ml) will be asked to fill out the EuroQol 5D (EQ-5D) and Kansas City Cardiomyopathy Questionnaire (KCCQ) – two quality of life (QoL) questionnaires validated for HF. Units: Mean scores, Mean change in scores/sub-scores, absolute and relative frequency distributions of QoL responders (in accordance to the patients' therapeutic regimens at baseline and after specialist referral) Time frame: Baseline (Visit 1) and Visit 2 and Visit 3	Section 9.5.1

3 Investigational plan

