Considering of the above assumptions, a number of 2,160 patients who enter the prospective period of the study (i.e. referral to a cardiologist) is required. It is further assumed, based on unpublished data from chronic heart failure registries (data on file), that at least around 60% of patients treated by primary care physicians will have NT-proBNP levels ≥ 600 pg/ml at baseline. This in turn leads to the calculation that, in order to obtain 2,160 patients in the prospective period of the study, 3,600 consecutive patients will need to be enrolled for visit 1 (baseline).

Assuming an expected drop-out rate of 10% of patients, 4,000 patients will be enrolled of whom 2,400 will enter into the prospective period.

The sample size calculation was performed with nQuery Advisor version 7.0 'using Table POC0-1.

10 Ethical considerations

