 - Atrial fibrillation, Atrial flutter, Tachyarrhythmia, Diabetes mellitus Type 1, Diabetes mellitus Type 2, Obesity, Stable angina pectoris, Unstable angina pectoris, Asthma, Anemia, Depression, COPD, Renal disease – due to Hypertension, Renal disease – due to diabetes, Renal disease – Other, Hypertension, Carotid artery stenosis, Renal artery stenosis, Dyslipidemia, Primary hyperaldosteronism, Hyperthyroidism, Hypothyroidism, Peripheral vascular disease, Sleep apnea, Parkinson's disease, Alzheimer's disease, Peripheral neuropathy (any etiology), Dementia (other than Alzheimer's), Rheumatoid arthritis, Osteoporosis, Alcoholic liver disease, B chronic hepatitis, C chronic hepatitis, Steatohepatitis (Absent, Absent – Prior present, Present, Present – New, Present – No Change, Present - Worse)
 - Transient ischemic attack, Venous thromboembolism, Angioedema, New malignant disease (Absent, Present)
 - Previous/current malignant disease (Better, No Change, Worse)

Pharmacological treatment of HF

- ATC level 2 of HF medication at Visit 1, Visit 2 and Visit 3.
- Preferred name of HF medication at Visit 1, Visit 2 and Visit 3.
- Dose and frequency of HF medication
- Duration of HF medication at Visit 1 in groups (≤ 1 year, > 1 year to ≤ 2 years, > 2 year to ≤ 3 years, > 3 years);

NT-proBNP, stability and suitability for prospective interventional period

- NT-proBNP ever tested before Visit 1 (Yes, No)
- NT-proBNP in pg/ml at Visit 1 and Visit 3.
- NT-proBNP in groups (≥ 600 to < 800 pg/ml, ≥ 800 to < 999 pg/ml, ≥ 1000 to < 1200 pg/ml, ≥ 1200 pg/ml) at Visit 1 and Visit 3.
- Absolute Change in NT-proBNP between Visit 1 and Visit 3 (change calculated via *post minus pre value*)
- Clinical stability of the patient at Visit 1 (Yes, No)

[figure not shown]
- Suitability for prospective interventional period of the study (Yes, No)
- Referral to cardiologist (Yes, No)
- Reason for non-referral to cardiologist

[figure not shown]
Cardiologist's advice

- Cardiologist's advice on therapy level (No change, Dose reduction, Dose increase, Discontinuation, New prescription)
- Cardiologist's advice on patient level (No change, Treatment intensification, Treatment reduction, Treatment adaption)
- Implementation of treatment changes by cardiologist (Yes, No, Partially)
- Acceptance of cardiologist's advice by primary care physician on therapy level (Yes, No)

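### NT-proBNP change is planned only as a raw difference by adherence stratum, although the reading that admits a patient is also the baseline: a fall is expected in every stratum without any effect of optimization

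*SAP*

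**What the plan says.** The Protocol summary states that only patients judged clinically stable "who show NT-proBNP blood levels ≥ 600 pg/ml will enter the prospective period of the study". Protocol Table 2-1 confirms that for these patients "two NT-proBNP measurements will be available: at baseline and at visit 3", so the qualifying value is also the pre-value. Protocol 5.3 describes a single-arm study without randomization.

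SAP 6.2 lists "Absolute Change in NT-proBNP between Visit 1 and Visit 3", calculated as post minus pre. SAP 7.6 says that summary statistics for both visits and "the absolute change from Visit 1 to Visit 3 will be provided", in the Follow-up Set and by the four combinations of adherence before and after referral. Under SAP 7.1 these statistics include the mean, SD, median and range. Protocol 9.5.3 adds counts of patients whose level rose or fell. For readings reported only as below a limit, SAP 7.6 says that "the new value XX-1 pg/ml will be used for the analysis"; readings above a limit become XX+1.

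Neither document plans a log scale, a ratio or a baseline-adjusted comparison for NT-proBNP, and neither mentions regression to the mean. The deviations listed in SAP 7.13 do not touch the point.

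The objective is worded in two ways. In Protocol 2.2 and SAP 3.2 it is to characterize how optimization "affects NT-proBNP levels in clinically stable CHF patients with baseline NT-proBNP levels" at or above 600 pg/ml. In Protocol Table 2-1 it is to demonstrate that optimization "will lead to clinically relevant decrease of NT-proBNP levels in" the same patients.

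**The concern.** Someone admitted because one reading was above a threshold will, on average, read lower next time. Here the change is measured from that same reading and no unselected or untreated group shows how far values would have drifted anyway. The stratified change table is the only analysis offered for an objective worded as an effect. A fall in the stratum that moved from non-adherent to adherent treatment could easily be reported as the benefit of optimization, and the Table 2-1 wording invites that.

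A second, separate matter is scale. If the marker is right-skewed, as assumed here, a mean difference in pg/ml is weighted toward the few patients with very high values. It describes proportional change poorly.

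**Working it through.** The documents give no SD, correlation or expected change for NT-proBNP, so there is no figure of the plan's own to reproduce. The size is worked out under a true effect of zero.

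**Inputs**
- Threshold 600 pg/ml (Protocol summary).
- Share above the threshold 0.60: Protocol 9.8 assumes "at least around 60% of patients treated by primary care physicians will have NT-proBNP levels ≥ 600 pg/ml at baseline".
- Assumed, not in the documents: lognormal values with the same distribution at both visits, log SD *s* = 0.8 to 1.2, log-scale correlation *r* = 0.7 to 0.9.

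**Step 1: the fall common to all strata.** The standardized cut-off is c = −0.2533 (40th percentile). The selected patients lie on average φ(c)/0.60 = 0.3863/0.60 = 0.6439 SD above the population mean at Visit 1, but only *r* × 0.6439 SD above it at Visit 3. Hence

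ratio (Visit 3/Visit 1) = exp[−(1 − r) × s × 0.6439]

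- s = 0.8, r = 0.9: exp(−0.0515) = 0.950
- s = 1.0, r = 0.8: exp(−0.1288) = 0.879
- s = 1.2, r = 0.7: exp(−0.2318) = 0.793

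**Step 2: the same fall in pg/ml.** With M = exp(ln 600 − s·c + s²/2), the selected mean is M·Φ(s − c)/0.60 at Visit 1 and M·Φ(rs − c)/0.60 at Visit 3. For s = 1.0, r = 0.8: M = 1274.5; Visit 1 = 1274.5 × 0.8950/0.60 = 1901; Visit 3 = 1274.5 × 0.8539/0.60 = 1814; change −87 pg/ml (−4.6%). Over the whole range the mean change runs from −32 to −178 pg/ml.

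Simulation with 2,000,000 draws per setting agrees. It adds a median change of −54 to −270 pg/ml (−145 in the middle case), 56 to 60% of patients falling, and 12 to 20% below 600 pg/ml at Visit 3. The concentration groups in SAP 7.6 start at 600 and have no category for those patients.

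**Step 3: differences between strata.** Selected patients were split into about 25% optimized and 75% not, with s = 1.0 and still no effect. The last two columns are optimized/not-optimized ratios; the truth is 1.

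| r | What drove optimization | Raw mean change, optimized / not (pg/ml) | Difference | Unadjusted log change | Log ANCOVA |
|---|---|---|---|---|---|
| 0.7 | unrelated to NT-proBNP | −136 / −140 | +4 | 1.002 | 1.002 |
| 0.7 | observed Visit 1 value | −410 / −43 | −367 | 0.902 | 0.999 |
| 0.7 | true underlying level | −97 / −153 | +56 | 1.088 | 1.172 |
| 0.8 | unrelated to NT-proBNP | −85 / −88 | +3 | 1.000 | 1.000 |
| 0.8 | observed Visit 1 value | −274 / −22 | −252 | 0.935 | 1.000 |
| 0.8 | true underlying level | −57 / −98 | +41 | 1.067 | 1.129 |
| 0.9 | unrelated to NT-proBNP | −42 / −41 | −1 | 1.000 | 1.000 |
| 0.9 | observed Visit 1 value | −137 / −8 | −129 | 0.968 | 1.002 |
| 0.9 | true underlying level | −25 / −47 | +22 | 1.036 | 1.070 |

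In both driven scenarios the optimized stratum starts higher (at r = 0.8, means of 2557 against 1669 and 2411 against 1719 pg/ml), yet the bias has opposite signs.

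**The case against.** The strongest defence is that no treatment effect is claimed. SAP 7.1 is descriptive, SAP 7.12 calls the study exploratory, and no test, interval or model is planned for NT-proBNP. Medians accompany means, which limits the pull of extreme values. Visit 1 values are tabulated by stratum, so baseline imbalance can be seen. The strata with unchanged adherence stand beside the optimized one, so a common fall would be visible as common.

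Most of this stands, and it limits the point to the interpretation of a secondary output. It does not remove it. The median does not protect against regression to the mean: in the middle case it falls by 145 pg/ml, more than the mean. Nothing in the SAP warns the reader, and the objective is still worded as an effect.

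Three stronger readings are tempting and not supported:
- *The raw scale causes the artefact and logging cures it.* Step 1 is on the log scale and the fall remains. The cause is selection on one reading in a single-arm study; logging addresses skewness only.
- *The contrast between strata must favour optimization, and baseline adjustment would correct it.* The documents do not establish what drives optimization. ANCOVA removes imbalance that follows the observed Visit 1 value, but enlarges the spurious ratio when optimization follows the true level (1.129 against 1.067 at r = 0.8).
- *The XX+1 rule materially truncates the change.* Neither document gives the device limit or how often it is exceeded, so the size cannot be worked out.

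**Conclusion.** The point holds for change within a stratum. With no effect at all, the planned tables should show a fall in every stratum: a geometric mean ratio of 0.79 to 0.95, a mean change of −32 to −178 pg/ml, and 56 to 60% of patients decreasing. These figures rest on the Protocol's 60% above threshold and on the assumed lognormal shape, log SD 0.8 to 1.2 and correlation 0.7 to 0.9. A higher correlation shrinks the fall; only perfect correlation removes it.

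For contrasts between strata the conclusion is weaker. They can be biased in either direction if baselines differ, and are unbiased if optimization is unrelated to NT-proBNP. The pg/ml differences in Step 3 are scenarios, not predictions. The primary analysis is unaffected. This is an inexpensive improvement to a secondary analysis.

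**What to change.** In SAP 7.6, or in the addendum that SAP 7.12 allows:

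1. Add the Visit 3/Visit 1 geometric mean ratio with 95% CI for each adherence stratum. Keep the raw pg/ml change and its median as a secondary display.
2. Add an exploratory comparison of strata on the log scale, shown both as unadjusted log change and as ANCOVA of log Visit 3 on log Visit 1, labelled as association. Note that ANCOVA removes only imbalance driven by the observed Visit 1 value and may increase bias if optimization followed the true level.
3. State that change within a stratum, on the raw or the ratio scale, includes regression to the mean and cannot be attributed to optimization.
4. Report how many values were replaced by XX+1 or XX−1 at each visit.
5. Align the Table 2-1 verb (demonstrate a decrease) with characterize, as in Protocol 2.2 and SAP 3.2. SAP 4.2 says data collection stopped in March 2018, so a line in SAP 7.13 saying which wording governs the report would be a practical way to record this.

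The cost is a little more programming on data already collected, and results that are read as ratios rather than pg/ml. No new measurements are needed. The additions make the artefact explicit; no analysis of these two readings can remove it.
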